- iii) To describe virus shedding (quantity of infectious virus) and duration according to important patient sub-groups, notably adults and children, those with mild illness (community patients) and those with more severe disease (hospitalised patients)
- To determine if aerosol generating procedures (most likely to be performed on ITU) are associated with changes in the quantity of environmental contamination with live virus, either in relation to quantity or particle size, or distance from source.
- v) To investigate the possibility of estimating the number of influenza-infected individuals in an area by the quantity o influenza virus recovered in sewage influent.

Policy related (to provide scientific data suitable for policy refinement on):

- vi) 'Safety distances' around patients with pandemic and seasonal influenza
- vii) Appropriate use of respiratory personal protective equipment (RPPE) and infection control practices for pandemic and seasonal influenza, according to patient type, illness severity and time since symptom onset
- viii) Antiviral treatment duration for patients with pandemic influenza
- ix) To develop an alternative surveillance strategy for quantifying influenza infections in a community.

The primary objective of this study is to correlate the amount of virus detected in a patient's nose with that found in the environment around them and with the time since illness onset and symptom severity. The point being that so called 'virus shedding' studies that measure virus recovered from the nose do not actually define environmental contamination and hazard to others. To the best of our knowledge such work has not been done before. The study has the potential to address the issues of how, when and where in relation to virus transmission, all of which we believe could inform policy. By collecting stools, we can also correlate influenza shedding in the nose with the stool and thereby provide a mechanism for generating estimates of influenza in the stool to populate the sewage-based epidemiology model.

How – Are touched surfaces important in virus transmission and does respired air present a significant transmission route?

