- 4. In order to ensure that patients with relatively recent onset of symptoms are recruited we will set exclusion criteria of >48h after symptom onset for community cases (but aim for recruitment of cases who are within 24h of symptom onset); and > 96h after symptom onset for hospitalised cases (but aim for recruitment within 48h).

Study Management

The study will be managed from a central coordinating site (Nottingham University) by a project manager and administrator. Data will be collected on to source documents and CRFs by the clinical team. Data will subsequently be entered onto a database. All data will be stored at the

University of Nottingham and they will act as custodian of it. Data generated from CEH will be shared with the project team and stored along with the rest of the virus shedding data.

Duration of the study and participant involvement

Each participant's involvement with the study will last for up to 2 weeks. No further follow up of participants is planned. Enrolment will begin in August 2009 and will cease in October 2009. Processing of samples collected and data extraction will continue until February 2010

End of the Study

The end of the trial will follow the completion of the laboratory analysis of samples and subsequent data analysis and presentation.

9. Selection and withdrawal of participants

See Appendix 1 for study outline

Cases

We propose the study of small numbers of symptomatic pandemic influenza patients from four groups:

- i) Hospitalised adults
- ii) Hospitalised children (up to the age of 16 years)
- iii) Adults in their own homes
- iv) Children in their own homes (up to the age of 16 years)

We regard these four groups as the minimum desirable based on known differences in virus shedding and respiratory etiquette between adults and children and likely differences in symptom severity between patients managed in the community and those who require hospital admission.

Hospital cases once discharged will be followed up and further sampling will take place in the patient's own home with consent. Similarly if a community patient is admitted to hospital mid-way through sampling we would attempt to follow them up in hospital.

Recruitment

HOSPITAL CASES:

Hospital cases will be identified through the clinical teams looking after patients in the participating centres.. We will not receive personal information about patients or approach them until their consent for us to do so has been granted.

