11. STATISTICS

Proposed Sample Size

We will aim to recruit groups of about 25 patients with recent onset H1N1 influenza in each of the four main sub-groups identified under 'research methods'. Most statistical analysis will involve examining correlations between virus shedding and virus deposition in the environment. The figure below illustrates that sub-group sizes of 25, which also allow pooling of data by adults or children (50 per group) or the whole population gives high statistical power (>80%) to detect correlations of >0.55 in groups of size n=25, 0.4 in groups of size n=50, and 0.3 in groups of size n=100.

As regards the duration of virus shedding, these data will be primarily descriptive but it will be important to be able to make formal statistical comparisons of the duration of shedding between adults and children. However by pooling data into adults vs. children (n=50 per group) differences of 5 days (adults) vs. 6 days (children) (two tailed-test) could be detected with >80% provided that the coefficient of variation in shedding was 0.3 or less. For larger differences e.g. 5 days vs.7 days or 5 days vs. 8 days, the study is well powered to coefficients of variation up to 0.6.

Statistical Analysis

Virus Shedding Study Protocol Version 1.2, 27AUG2010

Page 28 of 38

We will perform a detailed descriptive analysis of the data. The symptom constellation of patients in the different groups will be presented. The mean (standard deviation, range) of the quantity of infectious virus in the patient, on surfaces and in the air will be plotted for each patient group and as a function of time since onset, symptom constellation and distance from source (when relevant). The mean (standard deviation, range) duration of shedding will also be plotted for each patient group and as a function of symptom constellation. For a better representation of inter-individual variation (which is expected to be important), we will also plot individual trajectories.

In a second stage, formal tests will be used to determine which outcomes are significantly associated / correlated. Statistical tests will also be implemented to compare the mean duration of shedding among children and adults as well as among mild and severe cases.

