In a third stage, a Generalized Linear Model with random effects will be used to determine the key predictors for the quantity of infectious virus in surfaces and in the air. A survival analysis will also be implemented to assess the key predictors for the duration of viral shedding.

Outcome Measures

- 1. Virus shedding and deposition as measured by virus culture and quantitative PCR. (Quantitative PCR and plaque assay of respiratory virus specimens (nasal swabs) from patients and surfaces and air around them). Virus shedding and deposition as measured by virus culture and quantitative PCR.
- 2. Daily symptom scores and patient temperature readings
- 3. Medication logs
- 4. Household/ward daily temperature and humidity logs

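### Stage two compares mean shedding duration, but some patients will have no observed end of shedding; the survival method already planned for stage three should carry both group comparisons

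*Protocol*

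**What the plan says.** Section 11 (Statistical Analysis, second stage), repeated in the Synopsis, fixes the comparison: "Statistical tests will also be implemented to compare the mean duration of shedding among children and adults as well as among mild and severe cases". The same section plots mean, SD and range of duration by patient group. The secondary objectives in section 6 define the severity groups as "those with mild illness (community patients) and those with more severe disease (hospitalised patients".

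The third stage returns to the same outcome: "A survival analysis will also be implemented to assess the key predictors for the duration of viral shedding". It does not list the predictors, and it is not named as the method for the two stage-two comparisons.

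Three features of the protocol leave durations incomplete:

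- **Discharge.** Section 9 (Cases): "Hospital cases once discharged will be followed up and further sampling will take place in the patient's own home with consent". Community patients admitted part-way are also to be followed into hospital, but only as an attempt.
- **Withdrawal.** Section 9 (Participant Withdrawal) allows withdrawal at any time and discontinuation for non-compliance. Data gathered up to then may still enter the analysis.
- **Caps.** The Synopsis and section 10 (Surface Swabbing) limit follow-up to 10 days for adults and 12 for children. Section 10 expects daily nasal swabs for about 8 days on average in adults.

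No section says what duration a patient still positive at the last swab receives.

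**The concern.** A raw mean treats every recorded duration as complete. For a patient last swabbed while positive, only a lower bound is known. Entering that bound as the duration shortens the group mean. Leaving the patient out tends to remove long shedders, because a longer duration is more likely to outlast sampling.

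If such loss were equally common in both groups, much of the error would cancel. It probably is not. The consent step at discharge applies to the group labelled severe, and the caps differ between adults and children. Section 9 expects hospital patients to clear virus more slowly, so losing their later swabs pushes the estimate against the difference the investigators anticipate. Sections 5 and 6 link shedding duration to protective equipment, isolation and antiviral policy, so an understated duration in hospital patients would matter.

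**Working it through.** **1. The plan's own figure.** Section 11 takes "by pooling data into adults vs. children (n=50 per group) differences of 5 days (adults) vs. 6 days (children) (two tailed-test"), with power above 80% "provided that the coefficient of variation in shedding was 0.3 or less". Alpha is not stated; 0.05 is assumed.

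- SDs: 0.3 × 5 = 1.5 and 0.3 × 6 = 1.8 days; root mean square √((2.25 + 3.24)/2) = 1.657.
- SE = 1.657 × √(2/50) = 0.331.
- Power = Φ(1/0.331 − 1.96) = Φ(1.06) ≈ 85.5%.

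The stated figure reproduces, with every duration fully observed.

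**2. False positives, mild versus severe.** Inputs: 50 per group, equal true means of 6 days, CV 0.3, log-normal durations read in whole days, a common 12-day window from onset. Assumed, because the protocol gives no rate: a share of hospital patients has no swabs after a day drawn uniformly from 3 to 7, independently of shedding.

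| Hospital patients stopping | Bias, last-swab scoring (days) | Rejects: last swab | Rejects: still-positive dropped |
|---|---|---|---|
| 0% | about 0 | 4% | 5% |
| 10% | −0.2 | 8% | 6% |
| 20% | −0.4 | 17% | 6% |
| 40% | −0.7 | 51% | 10% |

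The log-rank test rejects 4 to 5% of the time in this model.

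Hand check of the last-swab column: SE = √(2 × 1.8²/50) = 0.36 day, and the unrounded biases are −0.18, −0.36 and −0.71.

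- 10%: shift 0.18/0.36 = 0.5; Φ(−1.46) + Φ(−2.46) ≈ 8%.
- 20%: shift 0.36/0.36 = 1.0; Φ(−0.96) + Φ(−2.96) ≈ 17%.
- 40%: shift 0.71/0.36 = 1.97; Φ(0.01) ≈ 51%, the other tail being negligible.

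**3. A different model.** Gamma durations, a 10-day sampling cap, first swab on illness day 1–2 (community) or 1–4 (hospital), stopping 1–4 days after the first swab. With equal means of 6 days and CV 0.3, last-swab scoring rejects 6%, 15% and 52% at 0%, 20% and 40% stopping. At CV 0.6 the rates are 5%, 9% and 25%.

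With a true difference (mild 5, severe 6 days, CV 0.3):

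| Stopping | Last swab: estimate, power | Dropped: estimate, power | Log-rank power |
|---|---|---|---|
| 0% | +0.99 d, 85% | +0.96 d, 84% | 84% |
| 20% | +0.63 d, 44% | +0.86 d, 70% | 82% |
| 40% | +0.24 d, 11% | +0.70 d, 50% | 78% |

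**4. If stopping follows recovery.** Assuming the last swab falls within 2 days either side of clearance, and otherwise as in step 2, last-swab scoring rejects 5.4% (bias −0.12 day) at 20% stopping and 10% (bias −0.24 day) at 40%.

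**5. The caps alone.** Gamma durations from onset: at CV 0.3 and means of 5 and 6 days, 0.3% and 2.5% exceed day 10. At CV 0.6, the upper value in section 11 ("the study is well powered to coefficients of variation up to 0.6"), and means of 5 to 8 days, 7 to 28% exceed day 10 and 3 to 18% exceed day 12. These shares are upper limits: Appendix 2 counts sampling days from enrolment, which may be up to 48 h (community) or 96 h (hospital) after onset, so sampling reaches later illness days.

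**The case against.** **The protocol states no biased rule.** It names neither a t-test nor last-swab scoring nor exclusion, and a scoring rule commonly belongs in the SAP. A reader might infer that the planned test has a type I error other than 5%. The text does not support that; the error rates belong to scoring rules supplied here. What remains is that the protocol fixes a comparison of means. The two simple ways of computing that mean from incomplete follow-up are both biased, so an SAP following the text literally inherits the problem unless it adopts a censoring-aware mean.

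**A survival analysis is already planned.** A reader might call the two stages incompatible. They are better read as a simple comparison followed by a model. Age group and severity are natural predictors for that model, but they are not listed, and it does not replace the stage-two tests.

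**The size is assumed.** The protocol says discharged patients will be followed up, and inclusion requires willingness to be sampled, so refusal could be rare. At 0 to 10% stopping the excess is slight, and the 51% should not be read as typical.

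**The loss is not one-sided.** Withdrawal affects both groups, and follow-up of community patients who are admitted is only attempted. Section 8 puts admissions at about 5%, so imbalance remains likely but is not certain. A reader might add death as a further route; no section mentions it.

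**The remedy has its own assumption.** Log-rank holds its level only if stopping is unrelated to shedding within group. Discharge on recovery may break that.

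**Duration is a secondary matter.** Section 11 describes these data as mainly descriptive. That limits the weight of the point, but formal tests are still specified.

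**Conclusion.** The point holds in a limited form. The protocol commits to comparing mean durations while its own procedures leave some durations unobserved, and it gives no rule for them. Last-swab scoring and exclusion both bias the mild-versus-severe comparison when loss is commoner in hospital. The child-versus-adult comparison is exposed through the unequal caps, little at CV 0.3 with means of 5 to 6 days and more at CV 0.6.

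The size cannot be fixed from the document. It runs from none, with complete follow-up, to serious if about 40% of hospital patients stop early for reasons unrelated to shedding, and it is smaller if stopping follows recovery. The power statement is sound for 5 versus 6 days at CV 0.3, given complete durations. The change is worth making because a better method is already in the plan and only the wording has to move.

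**What to change.** In section 11 and the Synopsis, specify for both stage-two comparisons (children versus adults, mild versus severe) the survival approach already planned for stage three: a log-rank test or Cox model, or restricted mean duration over a common window from symptom onset. Censor patients still positive at their last swab at that swab. Report Kaplan-Meier estimates alongside the descriptive means, and count censored patients by reason and group. Add a sensitivity analysis for informative stopping at discharge.

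Cost: wording only, no new data. A hazard ratio or restricted mean replaces the raw mean difference on which the power statement is built, so that statement should be re-expressed. The power loss with complete durations is very small: about 94% against 95% for 5 versus 6.25 days at CV 0.3 and 50 per group.

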We will advertise in the local press for volunteers with flu like symptoms to take part in the study. The advert will invite people who have or who develop a flu-like illness to participate in a research study that aims to improve our understanding of how swine flu is transmitted between people. We will ask people who are interested in helping to call our research office. Preliminary details will be obtained to establish their potential eligibility and an appointment will then be made for a member of the research team to visit the patient at home. Advertising in this way should enable us to pick up patients early in their illness. Adverts will run once a week for 4 weeks depending on recruitments rates.

2. Antiviral Collection Points

A back up to our planned recruitment via the local media will be to recruit patients who have been diagnosed with swine flu and who have been issued with a 'prescription' for oseltamivir. When a patient's family member or 'flu friend' collects the medicine from a designated collection point, a leaflet will be given out that describes our study and invites people to take part. Interested patients will be asked to ring our research office for further information and we can then establish their eligibility.

This method of recruitment gives us access to a significant number of people already clinically confirmed to have swine flu. A drawback is that we would only be able to recruit patients taking

oseltamivir, i.e. we would not be study the natural course of infection in this group. Furthermore, by using this approach it may be that some cases have had symptoms for some time before we make contact with them.

We have the support of the director of Public Health for Nottingham PCT ([name]) for this recruitment mechanism.

3. University of Nottingham

We will make contact with both well and unwell (symptoms of acute respiratory infection) students at the University of Nottingham through the student health centre and university accommodation / halls of residence.

- Unwell students would be asked to take part and then assessed for study eligibility
- Contacts of unwell students would be sought and asked to take part if they become unwell
- Well students would be asked to contact us should they become unwell

Case definitions:

There are a number of options available to us in defining the patients we wish to recruit;

- 1. Formal virological diagnosis of novel influenza A or novel A(H1N1) swine flu

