- Near-patient test positive for influenza A or other substantive test positive for influenza A (including 'swine flu')
- Willing to participate and agrees to allow both nasal and environmental samples to be taken

Exclusion criteria:

- Illness for >48h (community cases)
- Illness for >96h (hospital cases)
- A negative for swine flu (as part of NHS care)
- Has taken part in influenza research involving an investigational medicinal product within the last 3 months

Randomization

Randomisation to the days of surface swabbing will occur. 50% of participants will have surface swabbing done on alternate days from the first visit whilst the other 50% will have swabbing done on alternate days from the second visit. Envelopes will contain instructions to 'swab from Day 1' or 'swab from Day 2' in a 1:1 ratio. The envelopes will be identical and number of them will be given to each study nurse who will open an envelope following enrolment of a participant.

Participant Withdrawal

Participation in this study may be discontinued for any of the following reasons:

- 1. The wish of the subject. A subject can withdraw from the study at any time, for any reason, without prejudice to their future medical care. Participants will be made aware (via the information sheet and consent form) that should they withdraw the data collected to date cannot be erased and may still be used in the final analysis.
- 2. Non compliance with study procedures.
- 3. If a patient has a virological test that is negative for swine flu as part of NHS care.
- 4. Investigator's decision that withdrawal from further participation would be in the subject's best interest.
- 5. Termination of the study by the Investigator or Sponsor.

Data will be collected on participants who are withdrawn with outlining the reason(s) for discontinuation.

Criteria for terminating the study

Termination of the study as a whole may result from new information regarding H1N1 or issues with study conduct (e.g. poor recruitment, loss of resources).

Informed consent

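### The planned test of mean shedding duration, mild (community) versus severe (hospitalised), ignores unequal entry windows that remove short shedders mainly from the hospital group

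*Protocol*

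**What the plan says.** Section 6 (Research Objectives) sets a secondary objective of describing shedding and its duration by sub-group, including "those with mild illness (community patients) and those with more severe disease (hospitalised patients"). Severity is therefore defined by setting.

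Section 9 (Inclusion and Exclusion criteria) requires of every participant: "Near-patient test positive for influenza A or other substantive test positive for influenza A". It excludes "Illness for >48h (community cases") and "Illness for >96h (hospital cases"). Section 8 (Research Methods) adds softer targets. For community cases the team will "aim for recruitment of cases who are within 24h of symptom onset". For hospital cases the limit and target are "> 96h after symptom onset for hospitalised cases (but aim for recruitment within 48h"). Section 8 also says that only test-positive patients go on to sampling.

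Section 11 (Statistical Analysis) then plans, as a second stage, tests to "compare the mean duration of shedding among children and adults as well as among mild and severe cases". A third stage adds a survival analysis of predictors of duration. Neither stage mentions the different entry windows, and the protocol does not say whether duration is counted from symptom onset or from first sample.

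**The concern.** A patient is in the comparison only if a test was positive at or before entry. If that test is taken at enrolment, someone who stopped shedding on day 3 can be a community case enrolled on day 1 but cannot be a hospital case enrolled on day 4. This is left truncation at times that differ between the two groups. A test of mean durations treats the enrolled patients as a fair sample of each group's durations, which they are not.

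With duration counted from onset, the distortion makes hospital cases look like longer shedders. Section 9 already expects a slower decline in hospital patients, so the planned test could not separate that hypothesis from the selection. Section 6 uses shedding duration to inform how long isolation and protective equipment are needed.

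**Working it through.** **The plan's own figure.** Section 11 gives power only for adults versus children: 5 versus 6 days, 50 per group, two-tailed, coefficient of variation (CV) 0.3, power above 80%. Taking SD = 0.3 × 5.5 = 1.65 and a 5% level (not stated, assumed), power = Φ(1 / (1.65 × √(2/50)) − 1.96) = Φ(3.03 − 1.96) = 86%. The figure reproduces. No power is stated for mild versus severe.

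**Inputs from the protocol.** Entry limits are 48 h and 96 h, and targets are 24 h and 48 h. There are about 25 patients in each of four groups, so 50 hospital and 50 community. CVs are 0.3 and 0.6, the two values in Section 11.

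**Assumptions.** Both groups have the same true duration distribution, lognormal with mean 5 days. Test positivity equals shedding, and the qualifying test is at entry. There is no censoring. The test is Welch's t-test, two-sided 5%.

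**Hand check at the limits.** For a lognormal with σ² = ln(1 + CV²) and μ = ln 5 − σ²/2, the mean among those still shedding at entry time e is

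5 × Φ(σ − z) / Φ(−z), with z = (ln e − μ)/σ.

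At CV 0.6, σ = 0.5545 and μ = 1.4557.
- Community, e = 2: z = −1.375. The share retained is 0.9155 (about 8% lost), and the mean is 5 × 0.9732/0.9155 = 5.31 days.
- Hospital, e = 4: z = −0.125. The share retained is 0.5498 (45% lost), and the mean is 5 × 0.7516/0.5498 = 6.84 days.
- Spurious difference: about 1.5 days.

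At CV 0.3 the losses are 0.1% and 27%, the means 5.01 and 5.60, and the difference 0.59 day. The loss is strongly unequal but occurs in both groups. Everyone entering at the limit is the extreme case.

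**Spread entry times (simulation, no true difference).**

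| Community entry | Hospital entry | CV | Spurious hospital excess, from onset | False-positive rate |
|---|---|---|---|---|
| uniform 0-2 d | uniform 0-4 d | 0.3 | +0.09 d | 6% |
| uniform 0-2 d | uniform 2-4 d | 0.3 | +0.18 d | 9% |
| uniform 0-2 d | uniform 0-4 d | 0.6 | +0.38 d | 10% |
| uniform 0-2 d | uniform 2-4 d | 0.6 | +0.88 d | 33% |
| 1 d (target) | 2 d (target) | 0.3 | 0.0 d | 5% |
| 1 d (target) | 2 d (target) | 0.6 | +0.3 d | 8% |
| 2 d (limit) | 4 d (limit) | 0.3 | +0.59 d | 56% |
| 2 d (limit) | 4 d (limit) | 0.6 | +1.52 d | 74% |

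A gamma distribution gives similar results (at the targets with CV 0.6, +0.4 d and 12%). With the same 2-day entry in both groups the difference is 0 and the rejection rate about 5%.

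**Other time origin.** If duration is counted from enrolment, the sign reverses: about −0.4 to −1.8 days across the scenarios, because hospital cases have used up more of their shedding before being counted.

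**Check of the remedy.** A Cox model with delayed entry brought the false-positive rate back to about 5% (4.5-7.0% over 400 replicates).

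**The case against.** Several stronger readings are tempting, and the protocol does not support them.

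- *Short shedders are lost from the hospital group only.* The positive-test requirement applies to everyone. The community group also loses some, up to 8-13% at CV 0.6 with entry at 48 h (lognormal and gamma).
- *Every hospital case must be positive at enrolment.* The criterion also accepts another substantive test, and Section 9 notes that some patients may already have a PCR diagnosis. Such a test can predate enrolment, which weakens the selection for those patients.
- *Hospital cases will inevitably appear to shed longer.* That holds only from onset, and the origin is not stated. This does not rescue the test, since counting from enrolment biases it the other way.
- *The bias rivals the difference the study is sized for.* The 1-day difference belongs to adults versus children. That comparison is planned with 25 hospital and 25 community cases on each side, so entry windows are balanced by design and no bias is shown there.
- *Antiviral use confounds the comparison.* Of the antiviral collection-point route the protocol says: "A drawback is that we would only be able to recruit patients taking" oseltamivir. That is a back-up route and shows variation within the community group. Nothing in the protocol gives antiviral use in hospital cases, so an imbalance between the groups is possible but not shown.

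It is also fair to say that the duration data are called primarily descriptive, that late hospital entry and test-positive selection are acknowledged in Sections 8 and 9, and that an analysis plan not shown here could specify delayed entry. These points lower the severity. They do not remove the defect: the protocol names a comparison of means for these two groups, and the third-stage survival analysis is an additional search for predictors that does not replace it.

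**Conclusion.** The concern holds for the mild-versus-severe comparison of duration. As written, the test is subject to differential left truncation. From onset, with community entry uniform over 0-2 days and hospital entry over 0-4 or 2-4 days, the artefact is about 0.1-0.2 day (6-9% false positives) at CV 0.3 and 0.4-0.9 day (10-33%) at CV 0.6. If the 24 h and 48 h targets are met it is 0 to 0.3 day under the lognormal. The larger values need both wide variation and late hospital entry.

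The size depends on the assumed 5-day mean, the entry-time distributions, and test positivity standing for shedding. That the selection is unequal follows from the protocol's own entry rules. The direction depends on a time origin that the protocol leaves open. This is a should-fix for one secondary comparison. The correlation analyses and the adults-versus-children test are not affected on this ground.

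**What to change.** For mild versus severe only, replace the second-stage test of means with a survival comparison:

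- time origin at symptom onset, stated explicitly;
- delayed entry at the qualifying positive test or the first study swab, whichever is later, which also handles tests that predate enrolment;
- right censoring at the last swab for those still shedding;
- adjustment for age group, with logged antiviral use as a covariate or in a sensitivity analysis.

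Report the hazard ratio. Report medians or restricted means conditional on still shedding at a common landmark, for example 48 h. If few hospital cases enter early, hospital durations from onset are poorly identified, and an unconditional hospital median would rest on very few patients.

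Leave the adults-versus-children comparison unchanged on this ground.

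The cost is analysis wording. Onset time is needed to apply the entry criteria, and medication is already logged. The one item to confirm is that the date and time of the qualifying test are recorded.
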